### **10.3.2 Analysis of Baseline and Demographic Variables**

Descriptive summaries of demographic and Baseline characteristics for participants in the SS will be presented. For the dose escalation modules (Parts A, B and C) and the dose optimization module (Part A1), Baseline and demographic data will be tabulated by cohort and overall. For Part B and Part C, summaries may be presented by tumor type depending on the number of participants with specific tumor types. For the expansion modules (Parts D, E, F and G), participants will be tabulated by tumor type and overall.

### **10.3.3 Other analyses**

#### **10.3.3.1 Analysis of PK endpoints**

UCB6114 concentrations in blood will be listed for the SS and summarized descriptively for the PKS at each scheduled assessment by dose level. Where possible, key and other PK parameters will be determined after single and multiple doses using noncompartmental analysis and will also be summarized descriptively. Key and other PK parameters are described in [Table 10-1](#) and will be calculated where possible.

**Table 10-1: Pharmacokinetic parameters**

### 10.3.3.1.1 Dose dependency

The dose-dependency of PK parameters may be assessed.

### 10.3.3.1.2 Population PK

The PK of UCB6114 administered as monotherapy in Part A and Part A1 may be assessed using a population analysis approach. [REDACTED]

[figure not shown]
### 10.3.3.2 Analysis of genetic endpoints

Possible relationships between variations in DNA sequence and the PD effects of UCB6114 will be explored using summary statistics and graphs.

The analysis method and results for all genetic analysis will be reported separately to the main clinical study report.

### **10.3.3.3 Analysis of PD endpoints**

The PD variables from blood samples and optional tumor samples will be summarized descriptively by cancer type, dose level/schedule, treatment cycle, and overall. The relationship of PD variables with the tumor response to UCB6114 will be explored using summary statistics and graphs.

The analysis methods and results for all PD variables will be reported separately to the main clinical study report.

### **10.3.3.4 Analysis of biomarker endpoints**

Biomarkers examined in this study will be analyzed as described in Section [10.3.3.3](#).

### **10.3.3.5 Analysis of immunologic endpoints**

The ADA antibody status from the samples, participant classification according to ADA antibody status, changes from Baseline in titer over time, and the incidence of treatment-emergent ADA positivity will be summarized by timepoint. Potential relationships between ADA and PK, PD, antitumor activity, and safety will also be explored.

Hypersensitivity reactions are referenced in Section [10.3.1](#).

## **10.4 Planned efficacy/outcome analyses**

### **10.4.1 Analysis of antitumor activity/outcome endpoint**

The analysis of the primary antitumor activity/outcome endpoint in the expansion modules (Parts D, E, F, and G) will be the same as the analysis of the exploratory antitumor activity/outcome endpoints in the dose escalation modules and will be further described, as applicable, in a planned protocol amendment.

#### **10.4.1.1 Antitumor activity endpoint definitions**

The following are definitions of the antitumor activity endpoints:

Objective response rate (ORR) is defined as the percentage of participants with a best overall response (BOR) of complete response (CR) or partial response (PR).

Disease control rate (DCR) is defined as the percentage of participants with a BOR of CR, PR, or SD.

Best overall response is defined for each study participant as the best overall tumor response designation, as determined by the investigator according to relevant RECIST criteria, recorded between the first dosing date and the date of documented disease progression or the date of subsequent anticancer therapy (systemic medication, surgery, or radiotherapy for cancer), whichever occurs first. Complete response or PR determinations included in the BOR assessment

must be confirmed by a second scan  $\geq 4$  weeks after the criteria for response are first met. In addition, for a BOR of SD, tumor measurements must have met the criteria for stable disease (SD) at least once after the start of study treatment at a minimum interval of no less than 6 to 8 weeks. Table C in Section 11.9 (Appendix 9) provides the derivation of BOR when confirmation of CR and PR responses are required.

**Duration of response (DOR)** will be calculated for participants who achieve a CR or a PR and is defined as the time in days from the start date of the response to the first date that recurrent or progressive disease is objectively documented. For participants who die without objective disease progression, DOR will be censored on the date of death, regardless of cause. For participants who discontinue early without documented objective progressive disease, DOR will be censored at the date of their last available (scheduled or unscheduled) tumor assessment at which a lack of objective disease progression was determined. A sensitivity analysis will be performed taking into account both objective progressive disease and clinical disease progression, as determined by the investigator, in the calculation of DOR.

**Progression-free survival (PFS)** is defined as the time in days from first dosing date to the date of the first documented objective disease progression or death due to any cause, whichever occurs first. Participants who died without a documented objective disease progression will be considered to have progressed on the date of their death. Participants who did not progress or die will be censored on the date of their last available (scheduled or unscheduled) tumor assessment. Participants who did not have any on-study tumor assessments and did not die will be censored on the date of their first dose of study treatment. Participants who discontinued early without documented objective disease progression or death will be censored on the date of their last available (scheduled or unscheduled) tumor assessment at which a lack of objective disease progression was determined. Participants who started anti-cancer therapy without a prior documented objective disease progression will be censored on the date of their last available (scheduled or unscheduled) tumor assessment prior to the initiation of the subsequent anti-cancer therapy. A sensitivity analysis will be performed taking into account both objective progressive disease and clinical disease progression, as determined by the investigator, in the calculation of PFS.

**Overall Survival (OS)** is defined for all participants in the study as the time in days from the date of first dosing to the date of death from any cause. Participants will be followed up to ascertain their survival status at the SFU Visit (within 30 days after their final dose of study treatment) and at the Final Visit (3 months after their final dose of study treatment); they will not be followed up beyond this time point. For participants who discontinued early from the study or discontinued study treatment due to disease progression and were not known to have died, OS will be censored on the date of last contact.

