In Part C, eligible participants with unresectable locally advanced or metastatic colorectal adenocarcinoma, gastric adenocarcinoma, or adenocarcinoma of the gastroesophageal junction will receive UCB6114 as an iv infusion in combination with mFOLFOX6 chemotherapy. The initial dose and schedule of UCB6114 will depend on the dose level evaluated in Cohort 3 of Part A (anticipated to be 500mg Q2W iv), the emerging safety profile of UCB6114 monotherapy, and any predicted overlapping toxicities with mFOLFOX6. Up to 3 dose levels (anticipated to be 500mg, 1000mg, and 2000mg administered Q2W iv) are planned (Section 4.3.3). Up to 27 participants are planned. Dose escalation decisions in this module will be guided by a model-based estimation of the probability of DLT in cycle 1.

In the expansion modules, the RP2D from the respective escalation modules (Part A through Part C) will be tested either as monotherapy in selected tumor types (Part D and Part E) or in combination with SOC (Part F and Part G). Participants recruited to these modules must have at least 1 measurable tumor lesion according to relevant Response Evaluation Criteria in Solid Tumors (RECIST).

Participants will continue treatment until disease progression, unmanageable toxicity, criteria for discontinuation are met, or withdrawal of consent.

In the dose escalation modules, the decision to proceed to the next dose cohort will occur once all participants in the preceding cohort have been monitored for a minimum of 28 days (ie, 1 cycle). However, all available safety data (both within the cohort and from preceding cohorts) will be taken into consideration when dose escalation decisions are made.

In the expansion modules, response will be assessed after completion of 2 cycles of treatment (ie, 4 doses on Q2W dosing regimen) and at regular intervals thereafter.

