#### Type of participant and disease characteristics

- 2a. Participant has a histologically and/or cytologically confirmed diagnosis of one of the following advanced solid tumor types: colorectal adenocarcinoma, esophageal carcinoma, head and neck squamous cell carcinoma, lung adenocarcinoma, lung squamous cell carcinoma, pancreatic adenocarcinoma, prostate adenocarcinoma, stomach adenocarcinoma, bladder urothelial carcinoma, or breast invasive carcinoma.
- 3b. Participant has advanced disease (ie, unresectable locally recurrent or metastatic) and had access to approved therapies.
4. Participant has measurable or non-measurable disease as defined by the relevant RECIST (Appendix 9, Section 11.9).
5. Participant has a performance status of  $\leq 1$  on the Eastern Cooperative Oncology Group (ECOG) scale (Appendix 8, Section 11.8).
6. Participant has discontinued all previous therapies for cancer (with exception of treatments defined in Section 6.5.1), including chemotherapy, radiotherapy, cancer-related hormonal therapy, or other investigational therapy for a minimum of 28 days or 5 half-lives (whichever is shorter) (6 weeks for mitomycin-C or nitrosoureas) prior to study enrollment and recovered from the acute effects of therapy.

7. Participant has an estimated life expectancy of  $\geq 12$  weeks.
8. Participant has adequate bone marrow function, including the following:
  - a. Absolute neutrophil count  $\geq 1.5 \times 10^9/L$ .
  - b. Platelet count  $\geq 100 \times 10^9/L$ .
  - c. Hemoglobin  $\geq 9.0\text{g/dL}$  (or  $5.5\text{mmol/L}$ ).

Participants with hemoglobin  $\geq 8\text{g/dL}$  but  $<9\text{g/dL}$  may receive erythrocyte transfusions to achieve a hemoglobin level  $\geq 9.0\text{ g/dL}$ . Initial treatment must not begin until 2 days after the erythrocyte transfusion and after the confirmation of hemoglobin  $\geq 9.0\text{g/dL}$ .

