#### Type of participant and disease characteristics

2. Participant has histologically and/or cytologically confirmed diagnosis of one of the following advanced solid tumor types: colorectal adenocarcinoma, gastric adenocarcinoma, adenocarcinoma of the gastroesophageal junction, or pancreatic cancer.
3. Participant has advanced disease (ie, unresectable locally recurrent or metastatic).
4. Participant must have received and is refractory or intolerant to standard therapy appropriate for the tumor type.

---

5. Participant has measurable or non-measurable disease as defined by the relevant RECIST (Appendix 9, Section 11.9).
6. Participant has a performance status of  $\leq 1$  on the Eastern Cooperative Oncology Group (ECOG) scale (Appendix 8, Section 11.8).
7. Participant must have tumor lesion(s) or metastases amenable to biopsy, excluding bone metastases, as confirmed by a radiologist, if appropriate, and as deemed safe by the Investigator.
8. Participant must consent to the mandatory pretreatment and on-treatment tumor biopsies.
9. Participant has discontinued all previous therapies for cancer (with exception of treatments defined in Section 6.5.2), including chemotherapy, radiotherapy, cancer-related hormonal therapy, or other investigational therapy for a minimum of 28 days or 5 half-lives (whichever is shorter) (6 weeks for mitomycin-C or nitrosoureas) prior to start of study medication and recovered from the acute effects of therapy.
10. Any clinically significant treatment-related toxicity from prior therapy must have resolved to Grade  $\leq 1$  prior to study entry, with the exception of alopecia.
11. Participant has an estimated life expectancy of  $\geq 12$  weeks.

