## Type of participant and disease characteristics

2. Participant has a histologically and/or cytologically confirmed diagnosis of one of the following advanced solid tumor types: colorectal adenocarcinoma, gastric adenocarcinoma, or adenocarcinoma of the gastroesophageal junction.
- 3a. Participant has advanced disease (ie, unresectable locally advanced or metastatic).
- 4a. Participants must have received, or be intolerant to, or deemed not suitable for, at least 2 prior regimens of treatment, including the following standard of care anti-cancer treatments (where such treatments are available as standard of care):
  - a. Participants with colorectal cancer: fluoropyrimidine-, oxaliplatin-, and irinotecan-based chemotherapy, an anti-vascular endothelial growth factor biological therapy, and, if RAS wild-type, an anti-epidermal growth factor receptor (EGFR) therapy, or if microsatellite instability high/deficient mismatch repair (MSI-H/dMMR) immunotherapy (eg, nivolumab, pembrolizumab and ipilimumab).
  - b. Participants with gastric or gastroesophageal junction adenocarcinoma: fluoropyrimidine, a platinum, either a taxane or irinotecan, ramucirumab, and, if appropriate, human EGFR 2/neu-targeted therapy.
5. Participant has measurable or nonmeasurable disease as defined by the relevant RECIST.
6. Participant has a performance status of  $\leq 1$  on the ECOG scale.
7. Participant has discontinued all previous therapies for cancer (with exception of treatments defined in Section 6.5.3 ), including chemotherapy, radiotherapy, cancer-related hormonal therapy, or other investigational therapy for a minimum of 28 days or 5 half-lives (whichever is shorter) (6 weeks for mitomycin-C or nitrosoureas) prior to start of study medication and recovered from the acute effects of therapy.  
Any clinically significant treatment-related toxicity from prior therapy must have resolved to Grade  $\leq 1$  prior to study entry, with the exception of alopecia.
8. Participant has an estimated life expectancy of  $\geq 12$  weeks.

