**Table A Objective Response Status at each Evaluation for Participants with Nontarget Disease Only**

Nontarget diseases	New Lesions	Objective status
CR	No	CR
NonCR/nonprogressive disease	No	NonCR/nonprogressive disease
Indeterminate	No	Indeterminate
Unequivocal progression	Yes or No	progressive disease
Any	Yes	progressive disease

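### Exploratory DCR in Parts A, A1, B and C cannot credit lasting NonCR/nonprogressive disease in participants without measurable lesions, and the minimum interval for SD is given as two values

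*Protocol*

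**What the plan says.** **Eligibility.** Sections 5.1.1 (Part A) and 5.1.2 (Part A1) carry the criterion "Participant has measurable or non-measurable disease as defined by the relevant RECIST". Sections 5.1.3 (Part B) and 5.1.4 (Part C) carry the same one: "Participant has measurable or nonmeasurable disease as defined by the relevant RECIST". Only the expansion modules differ. Section 4.1 says of Parts D to G: "Participants recruited to these modules must have at least 1 measurable tumor lesion according to relevant Response Evaluation Criteria in Solid Tumors".

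**Endpoints.** Section 10.4.1.1 gives "Objective response rate (ORR) is defined as the percentage of participants with a best overall response (BOR) of complete response (CR) or partial response (PR" and "Disease control rate (DCR) is defined as the percentage of participants with a BOR of CR, PR, or SD". A best overall response of SD further requires that tumor measurements met the SD criteria at least once after the start of treatment, "at a minimum interval of no less than 6 to 8 weeks".

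**Response categories.** Section 11.9.1 classes all non-measurable disease as nontarget. Section 11.9.2 defines PR by the sum of diameters of target lesions. Table A, headed "Objective Response Status at each Evaluation for Participants with Nontarget Disease Only", offers four statuses: CR, NonCR/nonprogressive disease, Indeterminate and progressive disease.

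**Analysis sets.** Section 10.4.1.2 analyses antitumor activity on the Per-protocol Set, with the Safety Set as sensitivity. Section 10.1 puts no measurable-disease condition on either.

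**The concern.** The eligibility criteria let in a group for whom the response appendix provides a specific favourable status short of CR, and the DCR definition leaves that status out. A participant whose bone or effusion-only disease does not progress for many months would be scored the same way as one who progresses at the first scan.

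What is at stake is how the exploratory activity data read. Response is tabulated by dose level, dose levels hold few participants, and antitumor activity is one of the inputs to the recommended Phase 2 dose (Sections 4.1.2.5, 4.1.4.3 and 4.1.5.3). A DCR that drops because of lesion type rather than drug effect is hard to interpret there.

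The double value for the SD interval adds a second ambiguity to the same endpoint, and this one also reaches participants with measurable disease.

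**Working it through.** The protocol states no ORR or DCR figure for Parts A to C, so there is nothing to reproduce. The check traces the definitions and then sizes the effect.

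**1. Trace for a participant with nontarget disease only**

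- Eligible for Parts A, A1, B and C: yes.
- Has target lesions: no, because all non-measurable disease is nontarget.
- Can reach PR: no, because PR needs a fall in the sum of target diameters.
- Can reach SD: no, because Table A has no such status and the SD rule in Section 10.4.1.1 asks for tumor measurements.
- Can reach CR: yes.
- In the denominator: yes, in both the Per-protocol Set and the Safety Set.

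Table B does not help. Its SD row requires SD in target lesions. Its row for target lesions not assessed, with nonprogressive nontarget disease, returns Indeterminate, which is not disease control either.

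**2. Size of the DCR shortfall**

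Let q be the share of participants with nontarget disease only, and s the share of those with lasting NonCR/nonprogressive disease as best status. Then:

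shortfall in DCR = q × s

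Neither q nor s is in the protocol. Assume q from 10% to 30% and s = 50%:

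- 0.10 × 0.50 = 5 points
- 0.30 × 0.50 = 15 points

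In whole participants, assuming about 50% disease control in both groups:

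| Part and maximum N | Nontarget only | DCR as defined | DCR with the status counted |
|---|---|---|---|
| B or C, 27 | 3 (about 10%) | 12/27 = 44.4% | 14/27 = 51.9% |
| B or C, 27 | 8 (about 30%) | 10/27 = 37.0% | 14/27 = 51.9% |
| A, 42 | 13 (about 30%) | 14/42 = 33.3% | 20/42 = 47.6% |

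Rounding to whole participants moves these differences slightly away from q × s.

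Within one dose level or cohort of n participants, each such participant costs 1/n, whatever q is. That is 1/3 = 33.3 points at n = 3, 1/6 = 16.7 at n = 6, 1/8 = 12.5 at n = 8 and 1/9 = 11.1 at n = 9. These are the cohort or dose-level sizes that the protocol plans.

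**3. ORR, for comparison**

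Assume about 20% response in measurable disease and no CR in nontarget-only participants. With N = 27 and 3 nontarget-only, ORR is 5/27 = 18.5% over all against 5/24 = 20.8% in measurable disease. With 8 nontarget-only it is 4/27 = 14.8% (exact 95% CI 4.2 to 33.7) against 4/19 = 21.1% (6.1 to 45.6).

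**4. The SD interval against the scan schedule**

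- Part A (Table 1-4): first scan on Days 21 to 28 of Cycle 2, ±2 days. Study days run from 28 + 21 − 2 = 47 to 28 + 28 + 2 = 58.
- Parts A1, B and C: 8 weeks ±7 days from Day 1, so 56 − 7 = 49 to 56 + 7 = 63 days.
- Thresholds: 6 weeks = 42 days, 8 weeks = 56 days.

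Every on-schedule first scan passes at 6 weeks. Those in the earlier part of each window fail at 8. Five rows of Table C (CR then SD, progression or NE; PR then progression or NE) also turn on the minimum SD duration.

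**The case against.** **Exploratory endpoints.** In Parts A to C, ORR and DCR are tertiary, Section 10.2 rules out formal hypothesis testing there, and no escalation rule uses either rate. This stands, and it sets the severity. A reader might infer that dose selection is biased. The documents do not support that: antitumor activity is one element of a totality-of-data judgement, and small nonrandomized cohorts (spanning ten tumor types in Part A) are not strictly comparable in any case.

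**ORR denominator.** A reader might also infer that ORR is wrongly defined. It is not. Keeping all participants in the denominator is a legitimate, conservative convention, and nontarget-only participants can still count through CR. Restricting DOR to measurable disease would correct no denominator, because DOR covers responders only, and it would discard valid CR durations.

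**Table C.** Its lack of a NonCR/nonprogressive row proves little. It addresses confirmation of CR and PR, and has no row starting with SD or progressive disease either.

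**Left to the SAP.** Section 10.4.1.2 defers the full methodology to the SAPs, tabulates response data, and allows subgroups based on disease information. A SAP, which was not available here, could add a rule. But the protocol fixes the DCR definition itself, and that definition does not fit its own Table A.

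**Part A1.** Lesions there must be amenable to biopsy, excluding bone metastases (Section 5.1.2), so nontarget-only disease may be rarer in that part.

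**SD interval.** SD need be met only once, so an early first scan does not settle the matter. A participant still stable at the next scan qualifies under either threshold. Those affected are the ones with no later qualifying scan.

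**Conclusion.** The mismatch is real and follows from the protocol's wording alone. In Parts A, A1, B and C, a nontarget-only participant with lasting NonCR/nonprogressive disease counts in the DCR denominator and can never count in the numerator. The resulting shortfall is q × s: 5 to 15 points if q is 10% to 30% and s is 50%. Those shares are assumptions, and the actual effect could be nil if few such participants enrol.

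The two-valued SD interval is a secondary defect. It changes a best response only where a scan falls between 6 and 8 weeks and no later scan settles the matter.

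The point is minor. The endpoint is exploratory and untested in these parts, and the measurable-lesion requirement removes the DCR mismatch in Parts D to G, where ORR is primary. The interval wording would carry over to those parts if the same definitions are kept.

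**What to change.** In Section 10.4.1.1:

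1. For participants with nontarget disease only, count NonCR/nonprogressive disease that meets the minimum interval as disease control, and show it as its own best-response category.
2. Keep ORR and DOR on the stated analysis sets. Add a supportive ORR in participants with measurable disease at Baseline.
3. Replace the two-valued SD interval with one value no later than the earliest on-schedule first scan (about study Day 47), for example 6 weeks from first dose. Apply the same value where Table C refers to the minimum SD duration.

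The cost is a few lines of definition and one extra tabulation. No new data are needed, since Section 11.9.1 already classifies lesions as measurable or not at Baseline.

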#### **6.5.3 Permitted concomitant treatments (medications and therapies) during Part B**

The following concomitant medications and/or treatments are permitted during Part B of the study:

- Medications intended solely for supportive care (eg, treatments for nausea, vomiting, and diarrhea).
- Bisphosphonate therapy or therapy with RANK ligand inhibitor.
- Hormonal contraceptives/hormonal replacement therapy.
- Therapeutic use of steroids equivalent to prednisone  $\leq 10\text{mg/day}$ .
- Palliative radiotherapy to specific sites of disease is permitted if considered medically necessary by the investigator. Palliative radiotherapy specifically refers to radiotherapy symptom relief only.
- Participants who experience infusion-associated symptoms may be treated symptomatically as per standard practice.
- Granulocyte colony-stimulating factor (G-CSF) or pegylated G-CSF for the management of neutropenia related toxicities. (Note: prophylactic pegylated G-CSF in Cycle 1 is not permitted.)

---

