### **6.5.6 Prohibited concomitant treatments (medications and therapies) during Part A1**

The following concomitant medications are prohibited during Part A1 of the study:

- Any concurrent anticancer treatment within 28 days or 5 half-lives (whichever is shorter) prior to first dose of study medication (eg, cytoreductive therapy, radiotherapy [with the exception of palliative bone-directed radiotherapy], immunotherapy, biological therapy, or cytokine therapy [with the exception of erythropoietin])
- Any investigational drug within 28 days prior to start of study medication
- Herbal remedies or vitamins used as anticancer treatments
- Any herbal remedies with immunostimulating properties (eg, mistletoe extract) or known to potentially interfere with major organ function (eg, hypericin)
- Any anticoagulation therapy until after biopsies are obtained

Concomitant treatment considered necessary for the participant's well-being may be given at the discretion of the Investigator but should be discussed with the study physician or medically qualified designee whenever possible. If there is a clinical indication for one of these medications specifically prohibited during the study, discontinuation from the study medication may be required.

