### **6.5.7 Prohibited concomitant treatments (medications and therapies) during Part B**

The following concomitant medications are prohibited during Part B of the study:

- Any concurrent anticancer treatment within 28 days or 5 half-lives (whichever is shorter) prior to first dose of study medication (eg, cytoreductive therapy, radiotherapy, immunotherapy, biologic therapy, or cytokine therapy [with the exception of erythropoietin])
- Treatment with mitomycin C or nitrosoureas within 6 weeks of starting study medication
- Any investigational drug within 28 days prior to start of study medication
- Herbal remedies or vitamins used as anticancer treatments
- Any herbal remedies with immunostimulating properties (eg, mistletoe extract) or known to potentially interfere with major organ function (eg, hypericin)

Concomitant treatment considered necessary for the participant's well-being may be given at the discretion of the investigator but should be discussed with the study physician or medically qualified designee whenever possible. If there is a clinical indication for one of these medications specifically prohibited during the study, discontinuation from the study medication may be required.

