### 7.1.3 Other criteria for discontinuation of study medication

Participants must discontinue study treatment if they experience any of the following:

1. There is confirmation of a pregnancy during the study, as evidenced by a positive pregnancy test.
2. The participant experiences unacceptable toxicity.
  - For information on dose delays due to drug-related toxicity, see Section [6.6.1](#) (Part A and Part A1), Section [6.6.2](#) (Part B), and Section [6.6.3](#) (Part C). Participants will discontinue treatment, unless, in the opinion of the investigator, they are experiencing clinical benefit and it is in their best interest to continue treatment. For these participants, treatment may continue at a reduced dose at the discretion of the investigator and Sponsor.
3. The participant has documented evidence of progressive disease.
  - Participants with progressive disease before the end of Cycle 1 may be discontinued from study medication at the discretion of the investigator. Participants with progressive disease beyond Cycle 1 will be discontinued from study medication. In cases where progression is not clear and, in the opinion of the investigator, the participant may be having clinical benefit, the participant may continue treatment, but must be reimaged within 2 cycles of treatment.
4. The participant, for any reason, requires treatment with another therapeutic agent or modality for his/her cancer (with the exception of palliative bone-directed radiotherapy). In this case, discontinuation from the study treatment must occur before introduction of the new agent or modality.

---

5. Participant takes prohibited concomitant medications as defined in this protocol.

Participants who discontinue the study medication and/or study early will have end-of-study (SFU) procedures performed as shown in the Schedules of Activities for Part A ([Table 1-4](#)), Part A1 ([Table 1-5](#) and [Table 1-6](#)), Part B ([Table 1-7](#)), and Part C ([Table 1-8](#)).

See the Schedules of Activities for Part A ([Table 1-4](#)), Part A1 ([Table 1-5 and Table 1-6](#)), Part B ([Table 1-7](#)), and Part C ([Table 1-8](#)) for data to be collected at the time of study treatment discontinuation and follow-up and for any further evaluations that need to be completed.

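### In Parts A1, B and C, palliative radiotherapy outside bone is both permitted and a mandatory stop, and Section 10.4.1.1 does not except permitted radiotherapy from its BOR and PFS cut-offs

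*Protocol*

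**What the plan says.** **Permission.** For Part B, Protocol Section 6.5.3 states: "Palliative radiotherapy to specific sites of disease is permitted if considered medically necessary by the investigator". Sections 6.5.2 (Part A1) and 6.5.4 (Part C) say the same. None of the three limits the site to bone, and each adds that the term covers radiotherapy for symptom relief only.

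**Discontinuation.** Section 7.1.3 item 4 lists, among the events after which participants must stop study treatment, that the participant "requires treatment with another therapeutic agent or modality for his/her cancer (with the exception of palliative bone-directed radiotherapy"). It adds that "discontinuation from the study treatment must occur before introduction of the new agent or modality".

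**Prohibited lists.** In wording about the period before the first dose, Sections 6.5.6 to 6.5.8 give radiotherapy as an example of anticancer treatment. The Part A1 list has "radiotherapy [with the exception of palliative bone-directed radiotherapy"]. The Part B list has "cytoreductive therapy, radiotherapy, immunotherapy, biologic therapy, or cytokine therapy" with no palliative exception, and Part C matches it.

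**Endpoints.** Under Section 10.4.1.1, BOR counts assessments from first dose until documented progression or "the date of subsequent anticancer therapy (systemic medication, surgery, or radiotherapy for cancer), whichever occurs first". For PFS, "Participants who started anti-cancer therapy without a prior documented objective disease progression will be censored" at the last tumor assessment before the subsequent therapy began. Neither rule mentions radiotherapy that the protocol itself allows on treatment.

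**Lesion-level rule.** Appendix 9 (Section 11.9.2) makes target status indeterminate when a target lesion has been irradiated and has not reappeared or increased. The non-target rules there do not mention irradiation.

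**The concern.** There are two linked problems.

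The first is a contradiction in conduct. A participant in Part A1, B or C who needs palliative radiotherapy to a soft-tissue site may receive it and continue under Section 6.5, but must stop study treatment under Section 7.1.3. Sections 5 and 9 rule out waivers, so a site has no formal way to choose. Sites may act differently, and time on treatment and follow-up would then differ for reasons unrelated to the drug.

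The second is a gap in the endpoint definitions. Ending response follow-up and censoring PFS at a new anticancer therapy is a normal choice when the participant has left the regimen. Here the same cut-off can apply to someone who is still receiving study drug, is still scanned every 8 weeks, and has had only symptom-directed radiotherapy that the protocol allows. What is at stake is whether ORR, DCR and PFS include that participant's later assessments, and whether two programmers would derive the same values from the same data.

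**Working it through.** The protocol states no figure on this point, so the check sets the passages side by side.

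**Step 1: which radiotherapy is allowed on treatment?**

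| Palliative field | Sections 6.5.2 to 6.5.4 | Section 7.1.3 item 4 | Consistent? |
|---|---|---|---|
| Bone | permitted | excepted, treatment may continue | yes |
| Any other site | permitted | not excepted, treatment must stop | no |

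The conflict is confined to non-bone fields.

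**Step 2: does Section 10.4.1.1 except either row?** No. The BOR definition names radiotherapy for cancer and has no exception. The PFS sentence refers to anti-cancer therapy without naming radiotherapy. Three features of the text favour including it: the parenthesis in the BOR definition of the same section, the fact that Section 7.1.3 needs an exception for bone-directed palliative radiotherapy, and the listing of radiotherapy as anticancer treatment in Sections 6.5.6 to 6.5.8. None of these settles it.

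**Step 3: apply the rules literally to one case.** Take a Part B participant who has a painful rib irradiated in week 6, before the first scheduled scan at week 8, and stays on study drug. Sections 6.5.3 and 7.1.3 agree that this is allowed.

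- BOR: the window closes in week 6, so no on-treatment scan falls inside it. A partial response at week 8, confirmed at week 16, is not counted for ORR or DCR.
- PFS, if radiotherapy counts as anti-cancer therapy: a progression at week 16 is censored at the last assessment before week 6. That is the screening scan, so the participant contributes no follow-up time.
- A response first met and confirmed before the radiotherapy is kept.
- DOR: its definition has no rule for subsequent anticancer therapy. A responder confirmed before radiotherapy would still have a later progression counted in DOR, while PFS for the same person could be censored earlier.

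The gap therefore exists even in the row where the clinical passages agree.

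**Step 4: does Appendix 9 already cover this?** Only in part. The indeterminate rule applies to target lesions. Under Section 11.9.1, bone disease is nonmeasurable unless it has a measurable soft-tissue component, so the rib in Step 3 would usually be a non-target lesion. The appendix has no irradiation rule for those.

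**The case against.** The best defence is that the endpoint text can be read without any loss. *Subsequent* may mean after study treatment has ended, and radiotherapy for symptom relief only may not be radiotherapy for cancer at all. On that reading the participant in the example is followed normally. This stands as a possible reading, but the protocol does not adopt it. The need for an exception in Section 7.1.3 points the other way. What remains is an undefined rule rather than a proven loss of data.

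It is also fair that cutting BOR and PFS at new therapy is a legitimate pre-specified choice, and that further methodology is left to the module SAPs. That does not settle a conflict between two protocol sections, or a definition that names radiotherapy while other sections allow it.

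A reader might infer three stronger things that the documents do not support:

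- **That valid responses and progressions are certainly lost.** This depends on the reading just described, and for progressions also on extending the PFS sentence to radiotherapy.
- **That PFS will be overestimated by a definite amount.** Any bias depends on how closely the need for radiotherapy tracks impending progression. If the timing is unrelated to progression, the censoring causes no bias. The protocol gives neither that relation nor the frequency of radiotherapy.
- **That the primary ORR in Parts D to G is already affected.** Section 6.5 leaves their permitted treatments to later amendments. Section 10.4.1 carries the analysis over but says it will be further described in an amendment. The zero-response statements in Section 10.8.2 are context for the sample size and are not written as a stopping rule.

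**Conclusion.** The contradiction between Sections 6.5.2 to 6.5.4 and Section 7.1.3 item 4 is established from the text for non-bone palliative radiotherapy in Parts A1, B and C. The gap in Section 10.4.1.1 is also real: neither cut-off says whether permitted on-treatment palliative radiotherapy counts. Under a literal reading it discards later responses and confirmations, and under a wider reading of the PFS sentence it discards later progressions too.

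No size can be given. The effect depends on how many participants receive such radiotherapy, when they receive it, and to which lesions, and the protocol states none of these. ORR, DCR and PFS are tertiary/exploratory in Parts A1, B and C, and no formal hypothesis test is planned there. The point reaches the primary ORR in Parts D to G only if the later amendments both keep these definitions and permit palliative radiotherapy. It should be corrected now because the change is small and those amendments are still to be written.

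**What to change.** 1. Reconcile Sections 6.5.2 to 6.5.4 with Section 7.1.3 item 4, so that the radiotherapy permitted on treatment and the radiotherapy excepted from discontinuation are the same. Which clinical rule should prevail is for the sponsor and its clinical advisers.
2. State in Section 10.4.1.1 that palliative radiotherapy permitted by the protocol and given while study treatment continues is not subsequent anticancer therapy for BOR and PFS, so later scans and progressions count.
3. Keep the Appendix 9 indeterminate rule for irradiated target lesions, and state a matching rule for irradiated non-target lesions.
4. Carry the same wording into the amendments for Parts D to G if palliative radiotherapy is permitted there.

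The cost is a few sentences and no extra scans. The irradiated site and date must be identifiable in the data. The schedules of activities list concomitant medication, but no section says that the radiotherapy field is recorded, so this needs checking. Some assessments will become indeterminate, for example when the only target lesion was irradiated.
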